5.1 Drug information

5.1.1 Temozolomide

5.1.1.1 General information

Temozolomide is commercially available.

5.1.1.2 Packaging, dispensing and storage

Temozolomide is available as hard gelatin capsules (5mg, 20mg, 100mg, 250mg).

Temozolomide should be stored between +2°C - +30°C and protected from moisture.

Temozolomide should be administered in a fasting state at least one hour prior to eating.

5.1.1.3 Temozolomide accountability

The investigator/pharmacist must maintain an accurate record of dispensing of temozolomide in a drug accountability ledger, a copy of which must be given to EORTC at the end of the study. An accurate record of the date and amount of study drug dispensed to each patient must be available for inspection at any time.

5.2 Initial dose and schedule

5.2.1 Radiotherapy

Radiotherapy will consist of a conventionally fractionated regimen, delivering a total dose of 59.4 Gy in 6.5 weeks, in a once daily schedule of 1.8 Gy per fraction for a total of 33 fractions.

Treatment should start within 7 weeks of surgery and 8 days from randomization

A single phase treatment volume will be used throughout treatment – a cone-down or boost volume is not normally used (other than for shielding organs which have reached a tolerance limit e.g. optic chiasm at 55 Gy).

Whenever possible, target volume definition should be based on magnetic resonance imaging (MRI). Image fusion (= co-registration) of the MRI scans and the planning CT scan should be used for target volume definition. Centers having the possibility of image co-registration should use this technique for all trial patients. The accuracy of image co-registration should remain within < 0.5 cm. Post-operative imaging after resection and debulking is preferable.

CT-based 3-D treatment planning using beam's-eye-view and the registration of Dose-Volume-Histograms is mandatory for all centers.

5.2.1.1 Gross Tumor Volume

The Gross Tumor Volume (GTV) is defined by:

1. The entire region of high signal intensity on T2 weighted MRI images or FLAIR sequences (corresponding to the hypodense area on CT images).

Plus

2. The region of enhancement on post-operative CT/MRI if available or the region of enhancement on pre-operative CT/MRI if post op imaging is not available (usually contained in 1 above)

Plus

3. The tumor resection margin (usually contained in the above)

In some tumors no area of enhancement can be seen and the GTV is defined entirely on the T2 abnormality.

In case of complete or subtotal removal, the position of the tumor bed can have shifted, and the GTV should take the new position of the abnormalities on the planning CT scan and any post-operative imaging into account. Postoperative imaging is not mandatory, and it is acceptable to define GTV based on pre-operative scans and a planning CT.

5.2.1.2 Clinical Target Volume

The Clinical Target Volume (CTV) is defined by a 1.5 - 2 cm volumetric expansion of the GTV

The CTV extends to the contralateral hemisphere only when midline structures such as the corpus callosum and the contralateral hemisphere are invaded by tumor. The tentorium and meninges should be considered as anatomical borders and therefore a margin of 7-10 mm is sufficient to encompass the microscopic spread at these borders.

Volumetric expansion may also be reduced in areas adjacent to sensitive structures.

5.2.1.3 Planning Target Volume

The Planning Target Volume (PTV) will take into account uncertainties of planning and setup. This margin should be based upon known departmental values, but will usually be of the order of 0.5-0.7 cm.

All margins should be added using a three-dimensional (3-D) growth algorithm where possible.

5.2.1.4 Planning procedure

Patient either supine or prone depending on site of lesion, in an immobilization device (any fixation system with relocation accuracy < 5 mm).

The use of a Planning CT is mandatory. The use of a contrast medium, a maximum CT slice thickness of 3 mm in order to obtain good quality of Digitally Reconstructed Radiographs (DRR's) and margin definition is recommended.

Co-registration of CT and MRI data is strongly recommended for centers having implemented this function. For centers not having this possibility, a manual/visual fusion with the MRI shall be done.

Conventional or virtual simulation is mandatory. Planning with beams-eye-views (BEV's) of each beam is mandatory.

Use of shielding blocks or a multi-leaf collimator is mandatory.

Planning should conform to ICRU 50/62 criteria for target volume coverage, dose normalization and homogeneity. (Ref. 18)

5.2.1.5 Treatment technique

Treatment must be delivered with a linear accelerator with a minimal nominal beam energy of 4-6 MV. The volume should be treated by multiple field technique, all fields treated at each fraction.

The use of a vertex field is optional. If used it requires either a diagram or photograph of treatment position.

NOTE: the use of a strict vertex field may result in increased dose to the thyroid and whole body!

Treatment position verification is carried out by at least weekly portal imaging or portal films according to the institute's standards.

For 3DCRT: The prescription dose is specified and reported at the ICRU reference point as defined in ICRU Reports #50 and #62 [ICRU 1993; ICRU 1999].

For Intensity-modulated RT (IMRT): Treatment with IMRT is allowed provided that conventional fractionation and dose prescription according to ICRU #50 and #62 is used. No simultaneous integrated boost is allowed. IMRT will be allowed providing sufficient proof of external credentialing is submitted to and approved by EORTC QART team.

Stereotactic radiotherapy, implants, brachytherapy are NOT ALLOWED.

5.2.1.6 Acute toxicity and treatment interruption

Expected acute toxicity of conventional radiotherapy includes headache, fatigue, hair loss, skin reaction, sickness sometimes, mucositis (if nasopharynx included), temporary reduced hearing (if ear canal included), and temporary loss of taste (if nasopharynx included).

No dose adjustments are recommended irrespective of length of treatment interruptions.

Maximum overall treatment time: 7 weeks (theoretical optimal treatment time: 6.5 weeks).

Individual reasons for treatment interruption, such as major worsening of neurological or mental status or any other medical condition that would preclude the continuation of radiotherapy, and conversely the decision to resume radiation therapy after interruption, will be taken on an individual basis by the local investigator.

5.2.1.7 Dose prescription, fractionation

Dose prescription and recording will according to ICRU 62-criteria. Dose homogeneity requirements in the PTV shall be -5% + 7%. The PTV should be encompassed by the 95% isodose.

The 90% isodose is acceptable in close proximity to organs-at-risk.

Total dose: 59.4 Gy; dose per fraction: 1.8 Gy in 33 daily fractions

5.2.1.8 Dose Limitation to Critical Structures

Organs-at-risk to be spared if possible-are: eyes, pituitary gland, optic chiasm, optic nerves, brainstem, ear, uninvolved brain areas.

The optic chiasm, optic nerves and brainstem (= medulla, pons and midbrain) should not receive doses higher than 60 Gy.

The eye balls including the lens and retina should not be included in any direct beam. Maximum dose for the lens: < 5 Gy, for the retina: ≤ 36 Gy.

The normal brain contralateral to the tumor location may not receive > 60% of the total dose.

5.2.1.9 Dose reporting

The isodose distributions will be calculated and printed for documentation in three planes (transverse, coronal and sagittal planes) through the isocenter.

Isodose distributions with marked PTV and isodose lines with the maximum dose, 100%, 95%, 90%, 80%, 60%, 50%, 40%, 20% of the prescription dose should be reported for a reviewer to judge the adequacy of target coverage.

The following volumes should be calculated and documented in cm³: GTV, CTV, PTV and the total volume of the brain tissue (exclusive of PTV) as well as dose volume histograms of PTV and organs-at-risk.

Weekly portal imaging or portal films will be undertaken for set-up verification

5.2.1.10 Potential Late Complications

Depending on the tumor location and the region to be irradiated, several tissues or organs are potentially at risk for late damage, such as cortical brain, brain stem, chiasm, ear (mid or internal) and pituitary gland. All efforts should be made during planning to minimize the dose to critical structures. Late complications will be recorded according to CTC version 3.0

5.2.2 Temozolomide

5.2.2.1 Temozolomide randomization possibilities

Patients can be randomized to a) concomitant radiotherapy and temozolomide, b) adjuvant temozolomide, c) both or d) neither (this latter randomization should be understood as temozolomide chemotherapy at the time of progression).

5.2.2.2 Concomitant temozolomide dosing during radiotherapy treatment

Patients randomized to concomitant temozolomide will receive temozolomide continuously at a daily dose of 75 mg/m² during radiotherapy. The drug will be administered orally 1 hour before each session of radiotherapy during weekdays. During weekends without radiotherapy, the drug will be taken in the morning.

The dose administered will be determined using the body surface area (BSA) calculated at the beginning of the concomitant treatment. The daily dose will be rounded to the nearest 5 mg. In case of high value of BSA, an upper limit of 2.1 m² is suggested to calculate the dose. Patients should be told to swallow the whole capsules in rapid succession without chewing them. If vomiting occurs during the course of the treatment, no re-dosing of the patient is allowed before the next scheduled dose.

5.2.2.3 Resting period following radiotherapy treatment

The radiotherapy treatment is followed by a four weeks resting period.

5.2.2.4 Temozolomide dosing during adjuvant treatment

Patients randomized to adjuvant temozolomide will start adjuvant temozolomide after a 4 week resting period after the end of radiotherapy. Temozolomide will then be administered orally once a day for 5 consecutive days (days 1-5). The starting dose for the first cycle will be 150 mg/m²/day with a single dose escalation to 200mg/m²/day in subsequent cycles if no significant toxicity is observed in the first cycle. One cycle is defined as 28 days and a maximum of 12 cycles will be administered. Treatment can be discontinued earlier in case of significant toxicity interfering with further treatment and not responding to dose reductions, or at the patient wish.

The dose administered will be determined using the BSA calculated at the beginning of each treatment cycle. The dose will be rounded to the nearest 5 mg. In case of high value of BSA, an upper limit of 2.1 m² is suggested to calculate the dose. The exact dose administered should be recorded on the CRF. Each daily dose should be given with the least number of capsules. Patients should be instructed to fast 1 hour before and one hour after administration of temozolomide. Water is allowed during the fasting period. Patients should be told to swallow the whole capsules in rapid succession without chewing them. If vomiting occurs during the course of the treatment, no redosing of the patient is allowed before the next scheduled dose.

5.2.3 Summary of initial dosages and schedules

	Concomitant/RT	Adjuvant/year 1 after RT
RT	59.4 Gy, 6.5 weeks, 1.8 Gy/fractions, 33 fractions	None
TMZ	75mg/m ² /day, maximum 7 weeks	
TMZ		150-200mg/m ² /day, D1-5, every 28 days (maximum 12 cycles)

5.3 Treatment duration

The concomitant temozolomide is scheduled to last for 6.5 weeks according to the radiotherapy schedule during which temozolomide will be administered on a daily basis. In case of delays in the delivery of the radiotherapy temozolomide will be given for a maximum of 7 weeks. Adjuvant temozolomide treatment is planned for a maximum of 12 cycles.

Treatment should be administered until documented disease progression, unacceptable toxicity, patient refusal or further treatment not in patient's best interest or until the maximum treatment duration as specified in the protocol is reached.

5.4 Withdrawal criteria

Whatever the disease status, treatment will be discontinued in case of

- Patient refusal
- Unacceptable toxicity precluding further therapy
- Best interest of the patient

Patients discontinuing therapy in the absence of progression should usually not receive other cancer treatment before their disease progresses, unless this is clearly not in the interest of the patient.

After progression, further treatment will be at the discretion of the treating physician. Any anti-cancer therapy other than the study regimen described in this protocol will not be considered as part of the protocol treatment.

5.5 Dose and schedule modifications

5.5.1 General

In the general approach of the management of toxicities it is important to define to which drug the toxicities are related. After determination of the origin of the toxicity, the drug specific procedures have to be followed. For temozolomide these procedures are described in the following chapters.

If administration of temozolomide is interrupted due to unacceptable toxicities, the **patient must be evaluated at least once a week** following demonstration of the toxicity until **resolution** of the toxicity which should occur **within 14 days** allowing for re-treatment according to the guidelines below. These evaluations include: a physical examination, vital signs, hematologic tests, serum chemistries, and assessment of adverse events and concomitant medications.

5.5.2 Radiotherapy

With the type and site of radiotherapy foreseen in this protocol, interruption due to acute radiation toxicity is unlikely. Individual reasons, such as major worsening of neurological or mental status or any other medical condition that would preclude the continuation of radiotherapy and conversely the decision to resume radiation therapy after interruption will be taken on an individual basis by the local investigator.

For example, cranial irradiation can be withheld for CNS toxicity or ototoxicity greater than or equal to grade 3 attributable to radiotherapy. The overall time of interruption and over all time of radiotherapy must be recorded. Radiotherapy should not be interrupted due to haematologic toxicities or other temozolomide related toxicities. If radiotherapy is interrupted, actions regarding dosing on concomitant temozolomide are described hereunder.

- If the administration of temozolomide (see section 1.1.3) is interrupted, the radiotherapy will proceed normally and no catch up days of temozolomide will be given after the end of radiotherapy.
- The concomitant treatment will last until the end of radiotherapy and may be continued up to a maximum of 7 weeks. In case of radiotherapy delays, the duration of the concomitant treatment part will **never** exceeds 49 days.
- If radiotherapy is definitely stopped for toxicity, concomitant temozolomide is to be continued as per protocol unless progression occurs.

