Duration of treatment	
Concomitant temozolomide (arms 2 & 4)
 
The concomitant temozolomide is scheduled to last for 6.5 weeks according to the radiotherapy schedule during which temozolomide will be administered on a daily basis for a maximum of 7 weeks in case of radiotherapy delays.
 
Adjuvant temozolomide (arms 3 & 4)
 
One cycle is defined as 28 days and a maximum of 12 cycles will be administered.

Reference therapy, dose and mode of administration	
Radiotherapy (arm 1-4)
 
Radiotherapy will consist of a conventionally fractionated regimen, delivering a total dose of 59.4 Gy in 6 weeks 3days, in a once daily schedule of 1.8 Gy per fraction for a total of 33 fractions.

Criteria for evaluation	
Efficacy	
Overall survival (OS)
 
All patients will be followed until death. The duration of survival is the time interval between randomization and the date of death due to any cause. Patients not reported dead and lost of follow up will be censored on the date of their last visit.
 
Progression-free survival (PFS)
 
Disease progression is defined as radiological or neurological/clinical progression (whichever occurs first); progression free survival (PFS) is the time interval between the date of randomization and the date of disease progression or death whichever occurs first. If neither event has been observed, the patient is censored at the date of the last follow up examination
 
Neurological deterioration free survival
 
This study will assess neurological deterioration as a secondary endpoint to investigate if the prolongation of progression free survival translates into a better preservation of neurological function. Neurological deterioration is defined as a decrease in WHO performance status. Quality of Life analysis will also be used to assess neurological deterioration free progression.

Safety	
This study will use the International Common Terminology Criteria for Adverse Events (CTCAE), version 3.0, for toxicity and adverse event reporting.

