8.2.3.3 Analyses methods for safety endpoints

The safety analyses will be presented overall and by period as defined below:

- The baseline (BL) period will include all information recorded up to the randomization date.
- The radiation therapy (RT) or chemo/radiation period (RT&TMZ) will start on the day the radiation therapy is first given and end the day of the last administration of radiation therapy treatment plus 28 days.
- The adjuvant chemotherapy period (RT+TMZ) will start 29 days after the last dose of radiation therapy treatment and end-up 27 days after the first day of administration of the last cycle of adjuvant chemotherapy.
- The follow-up period (FUP) will start 29 days after the last dose of radiation therapy treatment or 28 days after the first day of administration of the last cycle of adjuvant chemotherapy.

The safety assessments include hematological toxicity, laboratory measurements and adverse events. Only the safety assessments performed before progression or within 7 days of progression and before start of any further anti-cancer therapy will be included in the analysis.

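### The rest period, adjuvant start and safety periods run only from the last radiotherapy dose, although concomitant temozolomide may outlast it; a very early radiotherapy stop then misfiles on-drug days

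*Combined protocol and SAP*

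**What the plan says.** **Concomitant course.** Under section 5.2.2.2, patients allocated to concomitant treatment "will receive temozolomide continuously at a daily dose of 75 mg/m² during radiotherapy". Section 5.3 adds: "The concomitant temozolomide is scheduled to last for 6.5 weeks according to the radiotherapy schedule", with a ceiling of 7 weeks if radiotherapy is delayed. Two consecutive bullets in 5.5.2 then deal with its end. One reads "The concomitant treatment will last until the end of radiotherapy and may be continued up to a maximum of 7 weeks". The next reads "If radiotherapy is definitely stopped for toxicity, concomitant temozolomide is to be continued as per protocol unless progression occurs".

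**What follows it.** Section 5.2.2.3 places a four-week rest after radiotherapy. Section 5.2.2.4 says that patients allocated to adjuvant treatment "will start adjuvant temozolomide after a 4 week resting period after the end of radiotherapy".

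**Safety periods.** In 8.2.3.3 the radiotherapy or chemo-radiation period (RT or RT&TMZ) ends 28 days after the last radiotherapy administration. The adjuvant period begins 29 days after the last radiotherapy dose. For patients without adjuvant treatment, "The follow-up period (FUP) will start 29 days after the last dose of radiation therapy treatment".

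None of these clocks refers to the last concomitant temozolomide dose.

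**The concern.** The period definitions work if radiotherapy and concomitant temozolomide end together. The last bullet of 5.5.2 creates patients for whom they do not. The temozolomide stopping table in 5.5.3.1 does not remove the case: it applies to toxicity related to temozolomide, whereas the example in 5.5.2 is severe CNS toxicity or ototoxicity attributed to radiotherapy.

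Two things follow. First, the treatment sections give no single answer for such a patient on when the daily course ends, when the rest begins and when adjuvant cycle 1 is due. Second, the by-period safety tables can place days on daily temozolomide, or the weeks just after it, under a later label. Arm 2 is the more awkward case. Its on-drug events would be labelled follow-up, and the worst-grade tables in 8.2.3.3.1 to 8.2.3.3.4 cover the treatment period as a whole, which the plan does not define. In arm 4 mainly the split between periods changes. The safety of concurrent and adjuvant temozolomide is a secondary objective (2.2), so the attribution should be right even where numbers are small.

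**Working it through.** **Inputs.** Radiotherapy is "59.4 Gy in 6.5 weeks, in a once daily schedule of 1.8 Gy per fraction for a total of 33 fractions" (5.2.1). The protocol summary gives the same course as "delivering a total dose of 59.4 Gy in 6 weeks 3days". The ceiling for concomitant temozolomide is 49 days (5.5.2). The rest is 28 days. The next safety period begins 29 days after the last radiotherapy dose.

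**The plan's own figure.** 33 × 1.8 Gy = 59.4 Gy. With a Monday start and weekday fractions, 30 fractions fill six weeks and the last three fall on days 43 to 45. So 6 weeks 3 days = 45 days, as stated.

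**Assumptions.** Monday start is day 1; radiotherapy is not resumed; temozolomide is not delayed; continuing as per protocol means the full scheduled course (last temozolomide day T = 45) or the ceiling (T = 49).

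**Formulas.** Let s be the last radiotherapy day.

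- RT&TMZ period ends: s + 28
- Adjuvant due (arm 4), and next safety period begins: s + 29
- On-drug days outside the RT&TMZ period: max(0, T − (s + 28))
- Drug-free days before adjuvant is due: max(0, s + 28 − T)
- Misfiling or overlap requires s + 29 ≤ T, so s ≤ 16 for T = 45 and s ≤ 20 for T = 49

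| Last fraction | Day s | Next period starts | On-drug days misfiled, T = 45 / 49 | Drug-free days, T = 45 / 49 |
|---|---|---|---|---|
| 1 | 1 | 30 | 16 / 20 | 0 / 0 |
| 5 | 5 | 34 | 12 / 16 | 0 / 0 |
| 10 | 12 | 41 | 5 / 9 | 0 / 0 |
| 12 | 16 | 45 | 1 / 5 | 0 / 0 |
| 13 | 17 | 46 | 0 / 4 | 0 / 0 |
| 15 | 19 | 48 | 0 / 2 | 2 / 0 |
| 16 | 22 | 51 | 0 / 0 | 5 / 1 |
| 20 | 26 | 55 | 0 / 0 | 9 / 5 |
| 25 | 33 | 62 | 0 / 0 | 16 / 12 |
| 33 (full course) | 45 | 74 | 0 / – | 28 / – |

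The limits correspond to at most 12 fractions (21.6 Gy) for T = 45. For T = 49 they correspond to at most 15 fractions (27.0 Gy), since day 20 is a Saturday and the last fraction before it is on day 19. A Thursday or Friday start puts the 33rd fraction on day 47 and the limit at 47 − 29 = day 18, inside the same range.

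**Later early stops.** From day 17 (T = 45) or day 21 (T = 49) no on-drug day leaves the RT&TMZ period, because the 28 added days absorb it. Temozolomide does run into the nominal rest, and the part of the 28-day post-drug window that stays in the RT&TMZ period is cut by T − s days. For s = 26 that is 45 − 26 = 19 days, which leaves 28 − 19 = 9 (at the ceiling, 49 − 26 = 23, which leaves 5).

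**The case against.** **The two 5.5.2 bullets may be compatible.** A reader might infer a flat contradiction, but the first bullet also allows continuation up to 7 weeks, so the second can be read as an instance of it. That stands. If instead the words tying the course to the end of radiotherapy govern, temozolomide stops with radiotherapy and neither timing problem arises, but the second bullet then has no effect. The text does not settle which reading applies.

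**The protocol does not order two courses together.** A reader might infer that it directs co-administration in arm 4. Section 5.2.2.4 starts adjuvant treatment after a resting period, and a patient still on daily drug has arguably not had one. The documents support ambiguity about the due date and no more.

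**The trigger is rare and treatment is over.** Section 5.5.2 calls interruption for acute radiation toxicity unlikely, and Appendix M states that all patients have completed study treatment. Rewording 5.5.2 now changes nobody's dosing. Both points stand. What remains live is the derivation in 8.2.3.3 and the record of what was done.

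**The harm is limited.** Safety is shown overall as well as by period, without formal comparison or p-values, and serious adverse events are collected to 30 days after the last protocol treatment (16.6). This also stands. It does not rescue the by-period rule, which as written gives the wrong label in the cases above.

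**Conclusion.** The gap is real and its reach is narrow. Misfiled on-drug days require a permanent radiotherapy stop for toxicity with a last fraction by day 16 (45-day course) or day 20 (49-day ceiling). They occur only in arms 2 and 4, and adjuvant treatment can fall due during the daily course only in arm 4. The size ranges from 1 day at the limit for a 45-day course to 16 days after a single fraction (20 at the ceiling). Every other early stop shortens the drug-free interval and the post-drug window without misfiling an on-drug day.

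Three stronger conclusions are not supported. Early stopping in general does not misfile on-drug toxicity. The toxicity of concurrent temozolomide cannot be said to be materially understated: no rate of early stops is given, so the number of patients affected cannot be computed, and few are expected. Nor are the affected patients shown to be those who tolerated temozolomide worst, since the trigger is a toxicity stop of radiotherapy, and 5.5.2 says that temozolomide-related toxicity should not interrupt radiotherapy.

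Overall survival, alpha, power and the event count are untouched. The result rests on the Monday start, no temozolomide delay, and the full-course reading of 5.5.2.

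**What to change.** **Treatment text.** The sponsor should reconcile 5.5.2 with 5.2.2.2 to 5.2.2.4 so that the end of the concomitant course, the rest and the adjuvant start are stated consistently after a definitive radiotherapy stop. No clinical rule is proposed here. As treatment is complete, the practical step is to document how any such patients were handled.

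**Section 8.2.3.3.** Use periods that neither overlap nor leave gaps:

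- Patients who started adjuvant temozolomide: the RT or RT&TMZ period ends the day before the actual first day of adjuvant cycle 1, and the adjuvant period starts on that day.
- All other patients: the RT or RT&TMZ period ends 28 days after the later of the last radiotherapy dose and the last concomitant temozolomide dose, and follow-up starts the next day.

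The actual cycle 1 date is needed as the boundary. Extending the first period to 28 days after the last dose and also starting the adjuvant period at cycle 1 would count days twice when cycle 1 came earlier, and lose days when it came later. If any arm 4 patient did receive both courses at once, those days would still carry the adjuvant label, so such patients should be listed.

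**Cost.** A few lines of text and one more date in the derivation. The CRF is not among the documents, so the availability of the last concomitant dose date should be confirmed. By-period counts may shift slightly; the overall survival and progression-free survival analyses do not change.
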